9.3 On Treatment Evaluations

9.3.1 Cycle 1 Day 1

- Concomitant medication review
- Vital signs, weight, BMI
- Physical examination including spleen size by palpation
- Selinexor dosing (level 0)

9.3.2 Cycle 1 Day 3

- Telephone call (or visit) to evaluate and/or adjust supportive care medications and adverse events

9.3.3 Cycle 1 Days 8 and 15

- Adverse events assessment and concomitant medication review
- Laboratory assessments:
 - Limited serum chemistry to include a CMP as defined in Section 9.1
 - CBC with differential (including reticulocytes if clinically indicated)
- MF symptom burden evaluation using the MPN-SAF TSS questionnaire (Appendix 7)
- Selinexor dosing (patients will be instructed to take their C1D8, C1D15, and C1D22 selinexor dose at home)

9.3.4 Cycle 1 Day 22

- Selinexor dosing (at home)
- Laboratory assessments:
 - CBC with differential (including reticulocytes if clinically indicated)

9.3.5 Cycle 2 Day 1 – Cycle 6 Day 1

- Adverse events assessment and concomitant medication review
- Vital signs, weight, BMI
- Physical examination including spleen size by palpation
- ECOG performance status (see Appendix 1)
- Optional Ophthalmologic exam (Appendix 2) *as clinically indicated*
- MF symptom burden evaluation using the MPN-SAF TSS questionnaire (Appendix 7)
- Laboratory assessments:
 - CBC with differential (including reticulocytes if clinically indicated)
 - Complete serum chemistry as defined in Section 9.1
- Peripheral blood sample for PDn analysis pre-dose and 4 hours post-dose (± 10 min) *at either C2D1 or C3D1*.
- Spleen volume will be measured by MRI (or CT abdomen if MRI is contraindicated) at the completion of 3 cycles and 6 cycles, allowing up to 4 weeks after cycle 7 D1. Imaging modality should remain consistent throughout study for each patient. Screening MRI should be completed ≤ 14 days prior to C1D1.
- 12-lead ECG *as clinically indicated*
- Selinexor dosing

9.3.6 Day 8 and 22 of each cycle from Cycle 2 through Cycle 6 (not clinic visit days)

- Selinexor dosing (at home)

9.3.7 Day 15 of each cycle from Cycle 2 through Cycle 6

- Selinexor dosing (at home)
- Laboratory assessments:
 - CBC with differential (including reticulocytes if clinically indicated)

9.4 Cycle 7 Day 1

- Adverse events assessment and concomitant medication review
- Vital signs, weight, BMI
- Physical examination including spleen size by palpation
- ECOG performance status (see Appendix 1)
- Optional Ophthalmologic exam (Appendix 2) *as clinically indicated*
- Bone marrow biopsy and aspiration: local testing for pathology reporting takes sample priority. However, when possible bone marrow biopsy and aspirate samples should be taken for correlative tests per [Section 14.1.1](#). The study team will follow instructions in the lab manual for shipping tissue for central review.
- MF symptom burden evaluation using the MPN-SAF TSS questionnaire (Appendix 7)
- Laboratory assessments:
 - CBC with differential (including reticulocytes if clinically indicated)
 - Complete serum chemistry as defined in Section 9.1

- MRI (or CT abdomen if MRI is contraindicated) for estimation of spleen volume. Imaging modality should remain consistent throughout study for each patient.
- IWG-MRT response assessment.
- 12-lead ECG *as clinically indicated*
- Selinexor dosing
- Peripheral blood samples for cytokine profiling
- Peripheral blood samples for evaluation of JAK2, MPL, and CALR mutant allele burden

Starting with cycle seven, patients will need to return to clinic every three months.

9.5 Cycle 10 + (every three months)

- Adverse events assessment and concomitant medication review
- Vital signs, weight, BMI
- Physical examination including spleen size by palpation
- ECOG performance status (see Appendix 1)
- Optional Ophthalmologic exam (Appendix 2) *as clinically indicated*
- MF symptom burden evaluation using the MPN-SAF TSS questionnaire (Appendix 7)
- Laboratory assessments:
 - CBC with differential (including reticulocytes if clinically indicated)
 - Complete serum chemistry as defined in Section 9.1
- 12-lead ECG *as clinically indicated*
- Selinexor dosing
- MRI (or CT abdomen if MRI is contraindicated) and IWG-MRT assessments will be performed for patients continuing on study treatment at cycle 10 D1, cycle 13 D1, and then every 6 cycles thereafter until treatment discontinuation to assess spleen volume and disease status.

9.6 End of Treatment Evaluations

The end of treatment visit will take place 7 days (+ 2 days) after the last dose of study drug and will include the following:

- Adverse events assessment and concomitant medication review
- Vital signs, weight, BMI
- Physical examination including spleen size by palpation
- ECOG performance status (see Appendix 1)
- Optional Ophthalmologic exam (Appendix 2)
- Laboratory assessments:
 - CBC with differential (including reticulocytes if clinically indicated)
 - Complete serum chemistry as defined in Section 9.1

- Coagulation tests to include PT, INR, and aPTT
- MRI (or CT abdomen if MRI is contraindicated) for estimation of spleen. Imaging modality should remain consistent throughout study for each patient. MRI need not be repeated at the EOT visit if one has been performed \leq 6 weeks
- IWG-MRT assessment
- 12-lead ECG
- MF symptom burden evaluation using the MPN-SAF TSS questionnaire (Appendix 7)
- Bone marrow biopsy and aspiration: local testing for pathology reporting takes sample priority. However, when possible bone marrow biopsy and aspirate samples should be taken for correlative tests per [Section 14.1.1](#). The study team will follow instructions in the lab manual for shipping tissue for central review.
- Peripheral blood samples for cytokine profiling
- Peripheral blood samples for evaluation of JAK2, MPL, and CALR mutant allele burden

9.7 Survival Follow Up

After treatment discontinuation, a telephone call will be made to the patient (or the patient's family) every 3 months to inquire about the patient's myelofibrosis disease status, general health, and information on any subsequent therapies utilized since discontinuation of study treatment for 24 months since the initiation of treatment. If available, medical records may be reviewed in lieu of a telephone call to the patient.

10 CRITERIA FOR EVALUATION AND ENDPOINT

10.1 Safety

Routine safety and tolerability will be evaluated from the results of reported signs and symptoms, scheduled physical examinations, vital sign measurements, and clinical laboratory test results. More frequent safety evaluations may be performed if clinically indicated or at the discretion of the investigator.

Physical Examination

Complete and symptom-directed physical examinations will be performed by a licensed physician (or physician's assistant or nurse practitioner).

Vital Signs

Vital signs (blood pressure, pulse rate, and temperature) will be obtained. Height, weight, and BMI will be obtained. ** Note: Height will be collected at the screening visit only. Screening height will be used to calculate BMI at all future visits.

Safety Laboratory Determinations

Laboratory evaluations will be performed as noted in the Study Calendar.

10.2 Efficacy

10.2.1 Radiographic Assessment of Efficacy

Volumetric measurements of the spleen will be obtained by MRI (or CT scans if MRI is contraindicated) as indicated on the Study Calendar.

A radiographic spleen response is defined per IWG-MRT criteria²⁶ as a $\geq 35\%$ volume reduction in the spleen (by MRI or CT), regardless of what is reported with physical examination. See Appendix 5 for details.

10.2.2 Efficacy Based on Patient Reported Outcomes

Subjects will complete the Myeloproliferative Neoplasm Symptom Assessment Form (MPN-SAF, see Appendix 7) at baseline and at each subsequent clinic visit (C1D8, C1D15, D1 of each subsequent cycle, EOT). Their Total Symptoms Score (TSS) will be calculated at each time point.

A symptoms response is defined per IWG-MRT criteria²⁶ as a $\geq 50\%$ reduction in the MPN-SAF TSS. See Appendix 5 for details.

10.2.3 Overall Response

Overall response criteria are based on the 2013 International Working Group-Myeloproliferative Neoplasms Research and Treatment (IWG-MRT) Criteria for myelofibrosis (listed in Appendix 5).²⁶

The overall response rate (CR, PR, CI) from after six cycles of treatment is defined in Appendix 5.

10.2.4 Overall Survival

Patients will be followed for 24 months from the initiation of study treatment. Overall survival will be assessed from initiation of study therapy to 24 months or death from any cause. Patients will be censored at 24 months.

10.3 Stopping Rules

10.3.1 Original Design

Up to 24 patients will be treated with the maximum tolerated dose of selinexor. Subjects will be enrolled in treatment cohorts of 8 subjects each and there will be a safety evaluation after each cohort has completed 1 cycle of treatment. Initially, 8 subjects will be enrolled in Cohort 1 and treated at a starting dose of 80 mg once weekly. The starting dose will be reduced by 1 dose level for all future patients after more than 2 patients in Cohort 1 require dose reduction for excess toxicity defined in section 7. Another set of up to 8 patients will be enrolled in Cohort 2. If more than 2 of 8 subjects in Cohort 2 (alone) require dose reduction for excess toxicity, then the starting dose will be reduced by 1 dose level in Cohort 3. Regardless of dose reduction, no cohort will ever contain more than 8 patients. The study will be discontinued if the starting dose for treatment cohorts is reduced more than 2 dose levels. Transition from dose level 1a to dose level -1 will not be considered a dose reduction.

10.3.2 Version 7 Update

After accrual of 12 patients, 7 patients required dose reduction to 40 mg once weekly. The decision was made to accrue the remaining patients at the lowest starting dose of 40 mg once weekly. Stopping rules do not apply after protocol version 7.

11 STATISTICAL CONSIDERATIONS

11.1 Statistical hypothesis

We hypothesize that treatment with selinexor will produce a clinically meaningful effect on the radiographic spleen response rate after six cycles of treatment.

11.2 Sample size determination

Response is defined as a 35% or greater reduction in spleen volume from baseline to after 6 cycles of treatment. A sample size of 18 evaluable subjects will provide 83% power at one-sided alpha = 0.05 to reject a response rate of 15% (the null hypothesis) using a one sample exact test for a binomial proportion provided the true response rate is 42%. The null hypothesis will be rejected if 6 or more out of 18 subjects respond. Patient who discontinued treatment and failed to receive 6 cycles of treatment would be considered as non-responders. The planned sample size is up to 24 to allow for up to a 25% dropout rate.

The alternative hypothesis is based on the known radiographic spleen response rate of ruxolitinib in MF patients and would indicate comparable efficacy.^{17,18} The radiographic spleen response rate of the standard therapy for patients who fail or can't tolerate ruxolitinib is unknown, and 15% was chosen as a response rate below the minimum clinically meaningful response rate.

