1 OBJECTIVES

1.1 Primary Objective

To assess the efficacy of selinexor on spleen volume reduction in subjects with myelofibrosis (PMF, PET-MF, or PPV-MF) refractory or intolerant to ruxolitinib and/or any other experimental JAK1/2 inhibitors.

Primary Endpoint:

Response rate defined as the proportion of subjects with $\geq 35\%$ reduction in spleen volume as measured by MRI or CT abdomen from baseline to after six cycles of treatment. Patients who do not complete six cycles of therapy will be considered non-responders, but their data will still be reported. Patients who do not complete six cycles of treatment will receive an MRI at cycle 7 day 1, or at discontinuation of therapy (see section 11.4.2).

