4.2 Number of Patients

The study will enroll up to 24 patients. The power calculation for efficacy is based on a sample size of 18 response-evaluable patients. The sample size was set to 24 to allow for enrollment of up to 6 patients who are not evaluable.

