11.3.2.1 Version 7 Update

After enrollment of 12 patients, 7 patients required dose reduction to 40 mg weekly. The decision was made to enroll the remaining 12 patients at the starting dose of 40 mg weekly.

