11.4.2 Evaluable for efficacy

The intent-to-treat population evaluable for efficacy includes all enrolled patients who received at least 1 dose of study medication.

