11.5 Statistical Analyses

11.5.1 Primary endpoint

The primary endpoint is defined as the proportion of subjects with $\geq 35\%$ reduction in spleen volume as measured by MRI or CT abdomen from baseline to after six cycles of treatment. A one sample test of binomial proportions will be performed at the one sided 0.05 significance level to test this hypothesis. The null hypothesis will be a response rate of 15% or less. Counts, proportions and 95% exact binomial confidence intervals (Clopper-Pearson) will be reported for each response category.

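### The 6-of-18 success rule and 83% power are set for 18 evaluable patients, but the efficacy set is every dosed patient, planned at up to 24

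*Combined protocol and SAP*

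**What the plan says.** Section 11.2 describes a one-sample exact binomial test of a 15% null rate at one-sided 0.05, with 83% power at a true rate of 42% and 18 evaluable subjects. Its decision rule is "The null hypothesis will be rejected if 6 or more out of 18 subjects respond". The Study Summary repeats the rule.

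The step from 18 to 24 is explained in two ways. Section 11.2: "The planned sample size is up to 24 to allow for up to a 25% dropout rate". Section 4.2: "The sample size was set to 24 to allow for enrollment of up to 6 patients who are not evaluable".

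The analysis set is defined differently. Section 11.4.2: "The intent-to-treat population evaluable for efficacy includes all enrolled patients who received at least 1 dose of study medication". Section 1.1, which points to 11.4.2, says: "Patients who do not complete six cycles of therapy will be considered non-responders, but their data will still be reported". Section 11.2 repeats this in the same paragraph as the 18-patient rule: "Patient who discontinued treatment and failed to receive 6 cycles of treatment would be considered as non-responders".

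Section 11.5.1 gives the test but no cut-off: "A one sample test of binomial proportions will be performed at the one sided 0.05 significance level to test this hypothesis".

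On numbers treated, section 11.3.1 reports 12 patients dosed by protocol version 7, and section 11.3.2.1 adds: "The decision was made to enroll the remaining 12 patients at the starting dose of 40 mg weekly".

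**The concern.** The sample-size text treats dropouts as patients who leave the denominator, so that 24 enrolled yields 18 analysed. The endpoint and population text keeps them in as failures, so that 24 dosed yields 24 analysed. Both cannot hold for a patient who takes a dose and then stops.

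This matters because it concerns the only formal success criterion of a single-arm, open-label trial. If the denominator is settled only after the responses are known, a result of 6 or 7 responders could be reported as a success on one reading and a failure on the other, each with support in the protocol.

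**Working it through.** **Inputs.** Section 11.2: null rate 0.15, alternative 0.42, one-sided alpha 0.05, exact binomial test, 18 evaluable, cut-off 6, dropout 25%. Sections 11.3.1 and 11.3.2.1: 12 dosed plus 12 to come, so 24.

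**Formula.** For n patients and cut-off c, the rejection probability at rate p is P(X ≥ c | n, p), the sum over k = c to n of C(n,k) p^k (1−p)^(n−k). Setting p = 0.15 gives the type I error (and the p-value for c observed responders); p = 0.42 gives power.

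**Step 1: reproduce the plan's figures.**
- P(X ≥ 5 | 18, 0.15) = 0.1206, too large.
- P(X ≥ 6 | 18, 0.15) = 0.0419, so 6 is the smallest valid cut-off.
- P(X ≥ 6 | 18, 0.42) = 0.8372, matching the stated 83%.
- 18 / (1 − 0.25) = 24.

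The arithmetic for 18 is right.

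**Step 2: use the section 11.4.2 denominator with 24 dosed.**
- P(X ≥ 6 | 24, 0.15) = 0.1394.
- P(X ≥ 7 | 24, 0.15) = 0.0572.
- P(X ≥ 8 | 24, 0.15) = 0.0199, so the cut-off is 8.
- P(X ≥ 8 | 24, 0.42) = 0.8575.

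**Step 3: same data, two denominators.** Suppose 24 are dosed and 18 complete six cycles.

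| Responders | p on 18 | p on 24 |
|---|---|---|
| 6 | 0.042 (success) | 0.139 (failure) |
| 7 | 0.012 (success) | 0.057 (failure) |

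**Step 4: exact cut-off by number dosed.** The last column shows the type I error if a count of 6 were kept.

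| n | Cut-off | Alpha | Power at 0.42 | Alpha with 6 |
|---|---|---|---|---|
| 16 | 6 | 0.0235 | 0.728 | 0.0235 |
| 17 | 6 | 0.0319 | 0.788 | 0.0319 |
| 18 | 6 | 0.0419 | 0.837 | 0.0419 |
| 19 | 7 | 0.0163 | 0.752 | 0.0537 |
| 20 | 7 | 0.0219 | 0.804 | 0.0673 |
| 21 | 7 | 0.0287 | 0.848 | 0.0827 |
| 22 | 7 | 0.0368 | 0.883 | 0.0999 |
| 23 | 7 | 0.0463 | 0.911 | 0.1189 |
| 24 | 8 | 0.0199 | 0.857 | 0.1394 |

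Below 16, the cut-off is 5 for n = 12 to 14 and 6 for n = 15. A count of 6 exceeds 0.05 at every n from 19 to 24.

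**Step 5: sensitivity to the meaning of 42%.** The documents do not say whether the rates describe all treated patients or completers. These are assumptions, not findings.
- If 42% is a completer rate and the null stays at 15% of all treated, the all-treated rate is 0.42 × (1 − d) for dropout d. Power of 8 of 24 is then 74% at d = 10% (rate 0.378), 59% at 20% (0.336) and 50% at 25% (0.315).
- If both are completer rates with 25% dropout, they become 0.15 × 0.75 = 0.1125 and 0.42 × 0.75 = 0.315. A cut-off of 6 of 24 then has alpha 0.046 and power 81.6%, but section 11.5.1 tests 15%, not 11.25%.

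**The case against.** The best defence is that the plan already rejects the completer denominator. Sections 1.1, 11.2 and 11.4.2 all keep early stoppers in, and section 11.5.1 fixes the null and the level. With the exact test named in 11.2, that determines the cut-off for any n, and the 6-of-18 rule simply describes n = 18. On this reading alpha is held, and power at 24 is slightly above the printed figure. No passage states a 6-of-24 rule. In addition, 24 is a ceiling, registration precedes treatment (section 12), and the extra six could be patients enrolled but never dosed, which would reconcile section 4.2 with 11.4.2.

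Much of this stands. An exact test on the actual number dosed keeps alpha at or below 0.05; 0.139 arises only if a count of 6 is carried over to 24. Loss of power is not established either, and since section 11.2 states the rates and the non-responder rule in one paragraph, the all-treated reading is the more natural.

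It does not remove the problem. Section 11.5.1 names neither an analysis set nor a cut-off, while the only explicit decision rule, printed twice, is for 18. The never-dosed reading fits poorly with section 11.2, which calls the extra patients dropouts, and with a record in which the first 12 accrued were all dosed and the other 12 are assigned a starting dose.

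**Conclusion.** The concern holds. It is an inconsistency between the sample-size statement and the analysis set, not a calculation error: the figures for 18 are correct but belong to a different denominator. The printed cut-off is valid only up to 18 dosed patients and too low at every number from 19 to 24. At 24 the cut-off is 8, with alpha 0.020 and power 86%; 6 or 7 responders would give opposite conclusions on the two denominators.

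The cut-offs rest on the 15% null, the exact one-sided 0.05 test and section 11.4.2 as written. The 86% also requires 42% to be an all-treated rate. If it is a completer rate with the null unchanged, power would be 50% to 74% for dropout of 25% down to 10%. Because the ambiguity affects the sole formal success criterion, it must be fixed before the primary analysis.

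**What to change.** Amend sections 4.2, 11.2, 11.5.1 and the Study Summary before the primary analysis:

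1. Name the section 11.4.2 set (all dosed patients) as the primary analysis set, with those who do not complete six cycles as non-responders.
2. State that the exact one-sided 0.05 test is applied to the actual number dosed, and list the cut-offs: at least 6 for 16 to 18, 7 for 19 to 23, 8 for 24. Adding 5 for 12 to 14 and 6 for 15 covers early closure.
3. State that 15% and 42% are all-treated rates, and give alpha 0.020 and power 86% for 24.
4. Remove the non-evaluable allowance for treated patients, or say that it covers only those enrolled but never dosed.
5. Close a neighbouring gap at the same time: count as a non-responder a patient who completes six cycles but lacks a usable baseline or cycle 7 day 1 scan. Sections 1.1 and 11.2 deal only with non-completers.

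The cost is wording, with no extra patients. The drawback is amending the success rule of an open-label trial after 12 patients have been treated. The amendment should therefore be dated and should state that the cut-offs follow from the exact test already specified and not from any observed responses.

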To date, 12 patients with myelofibrosis were dosed with selinexor in this study. The starting dose of selinexor was 80 mg weekly in the first six patients. After 3 out 6 patients required dose reduction due to grade 2 weight loss. The starting dose of selinexor was decreased to 60 mg weekly for subsequent patients. Additional six patients were enrolled at starting dose of 60 mg weekly. Of all the 12 patients, 7 required dose reduction to 40 mg weekly. Grade 2 weight loss occurred in 5 of 7 patients that required dose reduction to 40 mg weekly. At this time, 4 patients remain on selinexor treatment, 2 on 60 mg weekly dose and 2 on 40 weekly dose. The starting dose of selinexor will be decreased to 40 mg weekly for the remaining 12 expected patients.

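### The 25% dropout allowance does not offset early stopping when non-completers count as failures, so 6 of 18 and 83% do not describe the planned analysis of up to 24 patients

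*Combined protocol and SAP*

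**What the plan says.** The power statement in section 11.2 reads: "A sample size of 18 evaluable subjects will provide 83% power at one-sided alpha = 0.05 to reject a response rate of 15" percent, "using a one sample exact test for a binomial proportion provided the true response rate is 42" percent. The decision rule follows: "The null hypothesis will be rejected if 6 or more out of 18 subjects respond".

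The step from 18 to 24 is explained twice. Section 11.2 says "The planned sample size is up to 24 to allow for up to a 25% dropout rate", and the synopsis gives the same 25%. Section 4.2 says "The sample size was set to 24 to allow for enrollment of up to 6 patients who are not evaluable".

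Two other statements fix how early stopping is handled. Section 11.2 has "Patient who discontinued treatment and failed to receive 6 cycles of treatment would be considered as non-responders", and section 1.1 sets the same rule for the primary endpoint. Section 11.4.2 defines the population: "The intent-to-treat population evaluable for efficacy includes all enrolled patients who received at least 1 dose of study medication". Section 11.5.1 sets a one-sided 0.05 test against 15% but gives no cutoff for any denominator other than 18.

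On experience so far, section 2.3.3 reports 12 patients dosed, six starting at 80 mg and six at 60 mg, and then: "At this time, 4 patients remain on selinexor treatment, 2 on 60 mg weekly dose and 2 on 40 weekly dose". The remaining 12 are to start at 40 mg.

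**The concern.** A dropout allowance works when people who leave are removed from the denominator: enrol 24, lose 6, analyse 18. Here a dosed patient who stops early is not removed. That patient stays in and counts as a non-response. The six extra places then enlarge the denominator, and each early stop lowers the attainable response rate. The printed cutoff and power belong to an analysis of 18 that the population definition does not produce at full enrolment.

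The version 7 figures raise a second question. The starting dose was changed because of tolerability, and 4 of 12 patients were still on drug, yet the 25% was carried forward and no text connects the two.

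Two things are at stake. Applying 6 as the cutoff to 24 patients would inflate the type I error. If the true power is well below 83%, a non-rejection could be read as an inactive drug when it partly reflects patients who could not stay on treatment for six cycles.

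**Working it through.** **Inputs.** Null rate 15%, alternative 42%, one-sided 0.05, exact binomial test, cutoff 6 of 18, 25% allowance, N up to 24 (section 11.2). Six patients allowed as not evaluable (section 4.2). All dosed patients analysed (section 11.4.2). 12 dosed, 4 still on drug (section 2.3.3).

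**1. The plan's own figures reproduce.**
- P(X ≥ 6 | 18, 0.15) = 0.042 and P(X ≥ 6 | 18, 0.42) = 0.837, matching the stated 83%. A cutoff of 5 would give alpha 0.121, so 6 is right for 18.
- 18 / (1 − 0.25) = 24.

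The 83% is conditional on 18 analysed patients and does not use the dropout rate. Only N = 24 does.

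**2. Who leaves the denominator.** By section 11.4.2, only a patient enrolled but never dosed. All of the first 12 were dosed, so none of them leaves, whenever they stopped.

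**3. Cutoff for 24 dosed patients.** P(X ≥ c | 24, 0.15) is 0.139 at c = 6, 0.057 at c = 7 and 0.020 at c = 8. The smallest cutoff that holds 0.05 is 8.

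**4. Power with 8 of 24.** It depends on what the 42% means.
- All-dosed rate, non-completers already included: P(X ≥ 8 | 24, 0.42) = 0.857.
- Completer rate, with 25% not completing: the effective rate is 0.42 × 0.75 = 0.315, and P(X ≥ 8 | 24, 0.315) = 0.499.

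**5. What the first 12 could add.** By subtraction 12 − 4 = 8 are off drug (67%). Let k be the number of these who stopped before six cycles. The documents do not give k, so 0 to 8 is an assumed range. Taking 42% as the completer rate, responders are Bin(12 − k, 0.42) from the first 12 plus Bin(12, 0.42 × (1 − d)) from the last 12, where d is the early-stop rate in the last 12. Power is P(total ≥ 8):

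| k | d = 25% | d = 0 |
|---|---|---|
| 0 | 71% | 86% |
| 2 | 58% | 77% |
| 3 | 50% | 72% |
| 4 | 42% | 65% |
| 6 | 27% | 51% |
| 8 | 14% | 34% |

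The row k = 3 with d = 25% is the planned allowance throughout, and it agrees with the 50% in step 4.

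**6. Room left in the allowance.** If it is read as six early stops in 24, 6 − k remain for the last 12: three at k = 3, none at k = 6. It is already exceeded at k = 7 or 8.

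**The case against.** The strongest case against rests on four points.

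- **Off drug is not early dropout.** Treatment is open-ended after cycle 7 and the data cut-off is undated. Some of the 8 may have completed six cycles and stopped later. A reader might infer that 67% dropout has been observed against 25% planned. The documents do not support that: 8 of 12 is an upper bound, and neither timing nor reasons are given. This stands.
- **The observed rate may not carry over.** The first 12 started at 80 or 60 mg and the rest start at 40 mg. This also stands. It does not remove the first 12 from the primary analysis, where they are half of a full enrolment.
- **42% may be the all-dosed rate.** Section 11.2 calls it the true response rate in a paragraph that scores early stoppers as failures, and bases it on published ruxolitinib results. Power would then be 86%, above the stated 83%. This is a fair reading. Against it, adding six patients for dropout makes sense only if 42% applies to the 18 who remain. The text does not settle it.
- **Counting intolerance as failure is deliberate.** It is, and section 1.1 says that these patients' data will still be reported. The rule is not in dispute. The allowance, cutoff and power were not written to match it.

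**Conclusion.** The concern holds as an inconsistency within the sample size justification. The 25% allowance treats early stoppers as removable, while the analysis keeps them as failures. At 24 dosed patients the printed cutoff of 6 would give alpha 0.139, and the exact cutoff is 8. Power is 86% if 42% is the all-dosed rate and 50% if it is a completer rate with 25% non-completion.

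The drop to 50% arises at the planned 25%. It would be wrong to attribute it to the patients already off drug, or to say that their number disproves the 83%. Those data matter in a narrower way: they show that a figure was carried into version 7 with no sign of a check. On the completer reading with 25% early stopping in the last 12, power falls below 50% once k exceeds 3, and reaches 14% at k = 8. Whether k exceeds 3 cannot be told from the documents.

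These figures assume exact tests, full enrolment of 24 dosed patients, independent outcomes and, for the lower figures, a 42% rate among completers.

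**What to change.** In section 11.2, section 4.2 and the synopsis:

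1. Report how many of the first 12 patients stopped before completing six cycles.
2. State whether the 42% includes non-completers.
3. Replace 6 of 18 and 83% with the exact cutoff and power for the number of patients actually dosed. The exact cutoffs are 6 for 18 patients, 7 for 19 to 23, and 8 for 24.
4. Give that power across a stated range of non-completion for the 40 mg starters, for example from 25% to the early-stop rate observed in the first 12.
5. Drop or reword the allowance so that it covers only patients who leave the section 11.4.2 population.

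Keep N at 24, and report the six-cycle completion rate beside the primary result so that a non-rejection can be interpreted.

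The cost is wording and one tabulation of data already held. No patients are added. The stated power may become less favourable.
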